4. STUDY POPULATION

4.1 Population (base)

Participants will be recruited from a specialised centre for bipolar disorders of a large psychiatric hospital (GGzE, Centrum Bipolaire stoornissen). All patients who are referred to this service and all patients who 1) did not receive the current or a largely comparable psychoeducation program 1 year prior to start of the study and 2) who did not receive CBT-treatment tailored for bipolar disorder and with or without imagery interventions 1 year prior, are given written and oral information and informed consent forms and are invited to participate in this study. Currently there are 400 patients attending this service, at least 300 of those have not had psychoeducation or CBT in the last year. On average 70 new patients are referred to this specialised centre each year. Patients attending this service are aged between 18 and 65 years old, both male and female, mostly white European.

4.2 Inclusion criteria

In order to be eligible to participate in this study, a subject must meet all of the following criteria:

- Aged 18-68
- Sufficient Dutch language ability to permit the assessment to be completed.
- Diagnosis of BD (I or II or unspecified) according to DSM-5 (clinicians assessment).
- Willing to complete daily and weekly monitoring throughout the duration of the study.
- Successful completion of the daily monitoring in the 4 weeks active run-in phase.
- Willing to be randomised to either ImCT or psychoeducation condition
- Able to attending 12 consecutive weekly sessions ImCT or 6 weekly two hours sessions psychoeducation/TAU.

4.3 Exclusion criteria

A potential subject who meets any of the following criteria will be excluded from participation in this study:

- Learning difficulties, organic brain disease or severe neurological impairment.
- Have received either 1) psychoeducation similar to the presently used psychoeducation program, or 2) CBT tailored at bipolar disorder with or without imagery interventions within the last year prior to the start of the study.
- Current severe substance or alcohol misuse (clinicians assessment).

- Current manic episode as diagnosed by DSM-5
- Current active psychotic symptoms
- Presence of active suicidal risk as indicated by a score of 2 or more on item 12 (i.e. frequent thought and/or plans to end their life) of the QIDS (Rush et al., 2003) confirmed by convergent clinical opinion.
- Taking part in concurrent treatment studies investigating pharmacological or psychological treatment for BD.

4.4 Sample size calculation

To estimate the sample size needed for the between group design of this study, we used the study's primary outcome variable, mood variability, which is measured using the Affect Lability Scale (ALS-18).

The primary outcome variable for the between subjects design of the study, is the ALS-18, which was used in the audit (Hales et al., 2018) and in the pilot study by Holmes (Holmes et al., 2016). The effect sizes they found using the ALS-18 were $d = 0.8$ and $d = 0.99$ (see Table 1 below). We expect similar effect sizes in our study, that is $d = 0.9$ (the mean of the prior mentioned studies). Studies on the effect of psychoeducation have shown only moderate effects on medication adherence, knowledge of bipolar disorder and attitudes, but no or limited effect on mood variability or relapse, ranging from no effect (Bond & Anderson, 2015; Kurdal, Tanriverdi, & Savas, 2014) to a minimal effect (maximum of $d = 0.3$, but only in patients with less than 7 episodes), (Gumus, Buzlu, & Cakir, 2015; Morriss et al., 2016). We therefore expect an effect size of $d = 0.6$ (i.e., $d = 0.9$ minus $d = 0.3$). Based on prior mentioned effects of the ALS-18 we calculated the sample size needed, to power this study at 80% to detect an effect size of Cohen's $d = 0.6$ using a significance level of .05 two tailed T-tests using G*power 3.1.9.3 The calculated sample size needed is 45 in each group. The study of Holmes et al. (2016) showed a drop out 1 out of 15. After consulting with the research group from the audit and pilot study we expect a similar drop out rate in the current study. We therefore need a sample size of 48 in each group, 96 in total.

Table 1: Mean (SD) ALS-18 scores before and after ImCT in the pilot study of (Holmes et al., 2016)

Pre-Treatment	End of Treatment	4 week FU	12 week FU	24 week FU	Time	Pairwise differences, Bonferroni corrected pairwise t-test
46.36 (11.26)	35.54 (10.49)	35.43 (10.92)	36.36 (12.58)	34.71 (12.74)	F(4.48)= 6.75, $p < .001$	Pre vs 4w $t(12) = 3.77$, $p = .027$, $d = 0.99$; pre vs 12w

						$t(12)=3.58, p=.038, d = .84$; pre vs 24w $t(12)=4.62, p =.006, d = 0.97$
--	--	--	--	--	--	--

Next to the ALS-18 as primary measure, we also use daily mood variability scores, using the NIMH-LCM, for the within subjects-design. Here the assessment are compared between baseline (4 weeks is 28 measuring points) conditions and both treatment conditions (at least 6 weeks is 42 measuring points). As we use 70 measuring points in total only a small number of cases suffices to calculate and test differences scores. That is, for such a case series analyses, a sample size of 4 or more is sufficient (Barlow et al., 2009). Moreover, Bulte and Onghena (Bulte & Onghena, 2009) stress that to achieve a large effect size ($d = 1.5$) and a study powered at 80%, a study would need a minimum of 4 participants with a minimum of 20 measurements per person. Our study meets those requirements.

Finally, it is important to note that this is a feasibility study following an audit on ImCT (Hales et al., 2018), and a pilot study on ImCT (Holmes et al., 2016), and precedes and plans to inform a large upcoming ($N = 350$) RCT on ImCT in the UK next year. The National Institute for Health Research recommend sample sizes for a feasibility study of 30 in total (15 per arm) or a range of 24 to 50 in total (12 to 25 per arm) (Julious, 2005; Lancaster, Dodd, & Williamson, 2004; Sim & Lewis, 2012). Our study also meets those requirements.

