2. OBJECTIVES

Primary Objective and secondary objectives:

The present research project elaborates on a pilot study by Holmes and colleagues (2016) and an audit (Hales et al., 2018) using a new cognitive behavioural therapy enhanced with imagery techniques (ImCT), with an aim to improve the effectiveness of CBT for patients suffering from bipolar disorder. The pilot study (Holmes et al., 2016) found promising treatment effects but a controlled feasibility study is needed to test whether this treatment is more effective than regular treatment. Therefore, this research projects examines the effect of this new ImCT treatment, by comparing this intervention to psychoeducation treatment, one of the most regularly applied psychological intervention for bipolar disorder. The current

study will provide new insights for an upcoming large RCT evaluating the effectiveness of ImCT in the UK.

[figure not shown]
Our primary objective is to estimate the effects of ImCT compared to psychoeducation on mood variability. We hypothesise that (1) mood variability (primary outcome variable) will show stronger decreases in BD patients receiving ImCT at end of the intervention (T2), at follow-up measurement 8 weeks after concluding the interventions (T3) and at follow-up measurement 16 weeks after concluding the interventions (T4) than psychoeducation. Additionally, the effects of both treatments separately are also compared to baseline period preceding both treatments.

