3. STUDY DESIGN

The present research proposal concerns a randomised feasibility trial, comparing ImCT intervention to psychoeducation. In addition to the between group design, the study also uses a within-group design, where ImCT and psychoeducation is preceded by a four-week baseline condition. Note that during this baseline period and throughout the study, all patients will maintain their regular appointments with their psychiatrist or specialised nurse practitioner, who will prescribe, monitor and adjust mood stabilising medication conform guidelines. The within-group design allows participants baselines to act as their individual control periods with no intervention (Barlow, Nock, & Hersen, 2009; Bonsall, Wallace-Hadrill, Geddes, Goodwin, & Holmes, 2012; Holmes et al., 2016). The study will take place within a specialised centre for bipolar disorders within a large psychiatric hospital (GGzE). All participants start after 4 weeks of baseline with either ImCT or psychoeducation treatment. The duration of the study for participants will be 32 weeks for participants in the ImCT condition and 26 weeks for participants in the psycho-education condition. The difference in duration between the conditions is due to treatment length, that is, 12 weeks weekly 1-hour sessions for ImCT and 6 weeks weekly 2-hour sessions for the psychoeducation treatment. Note that all participants will have had 12 hours face-to-face contact in both conditions.

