6. METHODS

6.1 Study parameters/endpoints

6.1.1 Main study parameter/endpoint

To assess the primary endpoint of this study (1), decrease of mood variability, mood variability is measured using the Affect Lability Score Short Version (ALS-18) (Oliver & Simons, 2004) at baseline (T0), pre- intervention (T1) and post intervention (T2), and at follow-up measurements at 8 (T3) and 16 weeks (T4) after treatment discontinuation in both the ImCT and psychoeducation conditions. The ALS-18 is a self-report scale measuring lability in affect and consists of 18 items. Ratings are made on a 4-point scale with a maximum score of 72. Scores range from A= very characteristic of me (4 points), to D= very uncharacteristic of me (1 point).

In addition we monitor changes in mood variability using the National Institute of Mental Health Life Chart Methodology (NIMH-LCM) Prospective Self-Rating (Denicoff et al., 2000). Participants rate their mood (both mania and depression) on a 9-point Likert scale, ranging from -4 (severe depression, admission required due to severe dysfunction) to 0 (stable mood) to +4 (severe mania, admission required due to severe dysfunction). Daily measurements are calculated during a 4-week baseline prior to start of either ImCT or psychoeducation, during the intervention and until follow up at 16 weeks. This method is advised given that traditional self-report mood ratings over a single time point are scarcely representative of mood variability in bipolar disorder.

6.1.2 Secondary study parameters/endpoints (if applicable):

The following parameters are used for the following secondary objectives:

To assess (2a) level of depression, mania and anxiety and (2b) general functioning and hopelessness (3) number of relapses into mania or depression decline/increase, we administer the following measures:

- Level of depression, using the Quick Inventory of Depressive Symptoms (QIDS-SR) (Rush et al., 2003). The QIDS-SR is a 16-item self-report rating scale in which the nine DSM 5 symptoms of major depression are incorporated. Answers are rated on a four-point Likert scale (0-3). The QIDS-SR is administered weekly throughout the duration of the study.

- Level of mania, using the Altman Self-Rating Mania Scale (ASRM-NL) (Altman, Hedekker, & Peterson, 1997). The ASRM-NL is a 5 item self-report instrument to measure severity of mania symptoms. This is administered weekly throughout the duration of the study.

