8. STATISTICAL ANALYSIS

First, descriptive analyses will be used to establish mean scores, standard deviations and to identify outliers. Missing data from our primary outcome variable, will be listwise deleted. In our other outcome variables, data will only be included if pre- and post-measures are completed.

Second, the data will be checked with respect to violation of assumptions (such as error independency, non-normal distributions) for variance-based models.

Primary outcome variable: mood variability:

To assess if there is a stronger decrease in mood variability in the ImCT intervention condition as compared to the psychoeducation condition, multivariate repeated measures analyses are applied. Dependent variables are the scores on the ALS-18 (baseline, T0; pre-treatment, T1; post-treatment, T2; 8-weeks follow-up, T3; 16-weeks follow-up, T4) with treatment condition (ImCT, psychoeducation) as between subjects variable.

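### The 80% power in Section 4.4 belongs to one unadjusted t-test, whereas Section 8 plans an omnibus test with post hoc t-tests and names no single baseline-adjusted ALS-18 effect estimate

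*Combined protocol and SAP*

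**What the plan says.** Section 2 frames the aim as estimation: "Our primary objective is to estimate the effects of ImCT compared to psychoeducation on mood variability". Hypothesis (1) is that mood variability "will show stronger decreases in BD patients receiving ImCT at end of the intervention (T2"), and likewise at T3 and T4. The three visits are not ranked. Section 6.1.1 names no primary visit either.

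Section 4.4 takes the ALS-18 as the outcome for the between-group sample size, with d = 0.6 and 80% power, "using a significance level of .05 two tailed T-tests". The result is 45 per group, raised to 48 for dropout. It also says that the trial "precedes and plans to inform a large upcoming" RCT.

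In Section 8, for the ALS-18, "multivariate repeated measures analyses are applied. Dependent variables are the scores on the ALS-18" at T0, T1, T2, T3 and T4, "with treatment condition (ImCT, psychoeducation) as between subjects variable". The section goes on to say that these analyses establish an omnibus effect. Only if that is significant do post hoc tests follow, mostly independent t-tests, between groups and between time points, with Bonferroni correction. The number of tests in the correction is not given. Nor is it stated whether raw or change scores are compared. Gender and medication appear as covariates only in the regression of daily-mood entropy.

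Section 6.2 stratifies randomisation by mood-stabilising medication and calls this necessary because medication can affect the primary outcome.

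**The concern.** The stated power is attached to a test that Section 8 does not plan as its primary analysis. The t-tests that Section 8 does plan are conditional on the omnibus and run at a stricter level that cannot be computed from the text.

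The larger consequence is for estimation. A group-by-time omnibus on four degrees of freedom yields a p-value, not an effect with a confidence interval. The visit-level estimate to carry into the larger RCT would come from the post hoc stage. There the visit, the type of score and the Bonferroni divisor are all open, so the headline figure could be settled after the data are seen. The between-arm tests at that stage also make no stated use of the T1 score as a covariate, or of the stratum that Section 6.2 treats as important.

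**Working it through.** **Inputs from the documents.** Section 4.4: d = 0.6, two-sided alpha .05, n = 45 per arm; Table 1: pre-treatment ALS-18 SD 11.26.

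**Assumptions.** The documents give neither the correlation between visits nor the Bonferroni divisor. I use r = 0.3, 0.5, 0.7 and divisors 2, 3, 5. All figures take 45 complete patients per arm.

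**Step 1: reproduce the plan's figure.** Two-sample t-test, noncentrality d × √(n/2) = 0.6 × √22.5 = 2.85, df 88. Power is 80.4% at .05. So 45 per arm is one unadjusted two-sided t-test.

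**Step 2: the omnibus.** Section 8's stated aim is a stronger decrease, so I take the group-by-time test. Assume mean differences of 0, 0, 0.6, 0.6, 0.6 SD at T0 to T4 and compound symmetry. The mean is 0.36, and the squared deviations sum to 2 × 0.36² + 3 × 0.24² = 0.432. Noncentrality is (45 × 45/90) × 0.432/(1 − r) = 9.72/(1 − r), which is 13.9, 19.4, 32.4. With F on 4 and 85 df, power is 84%, 95%, 99.8%.

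**Step 3: one visit, three ways to compare the arms.**
- Raw score: effect 0.6, df 88.
- Change from T1: effect 0.6/√(2(1 − r)) = 0.507, 0.600, 0.775, df 88.
- T1 as covariate: effect 0.6/√(1 − r²) = 0.629, 0.693, 0.840, df 86 (T1 and stratum fitted).

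| Power at one visit | r = 0.3 | r = 0.5 | r = 0.7 |
|---|---|---|---|
| Raw, .05 | 80% | 80% | 80% |
| Raw, .05/3 | 66% | 66% | 66% |
| Change, .05 | 66% | 80% | 95% |
| Change, .05/3 | 49% | 66% | 89% |
| T1 covariate, .05 | 84% | 90% | 98% |
| T1 covariate, .05/3 | 71% | 80% | 94% |

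For raw scores, divisors 2, 3 and 5 give 71%, 66% and 59%.

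At .05 the covariate adds about 4, 10, 17 points over raw scores (83.9, 90.1, 97.6 minus 80.4). Over change scores it adds about 18, 10, 2 points (the same minus 66.2, 80.4, 95.3).

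**Step 4: precision.** The 95% CI half-width for raw scores is 1.987 × √(2/45) × 11.26 = 4.7 ALS-18 points. For change scores, multiply by √(2(1 − r)): 5.6, 4.7, 3.7. With T1 as covariate, multiply by √(1 − r²): 4.5, 4.1, 3.4.

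**Step 5: is the correlation range reasonable?** Table 1 gives means, SDs and paired t values. SD of the difference = mean difference × √n / t, and r = (s₁² + s₂² − s_diff²)/(2s₁s₂). At 4 weeks with n = 13: 10.93 × √13/3.77 = 10.45, so r = (11.26² + 10.92² − 10.45²)/(2 × 11.26 × 10.92) = 0.56. Over the three follow-ups, with 13 or 14 pairs, r runs from 0.52 to 0.72, with 95% Fisher intervals from about 0 to 0.91. That is too imprecise for a single value, hence the range.

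**Step 6: visit timing.** Section 3 gives "12 weeks weekly 1-hour sessions for ImCT and 6 weeks weekly 2-hour sessions for the psychoeducation treatment", and Section 6.1.1 sets follow-up "at follow-up measurements at 8 (T3) and 16 weeks (T4) after treatment discontinuation". Weeks since allocation at T2, T3, T4 are 12, 12 + 8 = 20, 12 + 16 = 28 for ImCT and 6, 6 + 8 = 14, 6 + 16 = 22 for psychoeducation. The arms are six weeks apart at every visit, and so in any average of visits.

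**The case against.** The strongest reply is that Section 8 does have a primary analysis. It is the omnibus, and by Step 2 its power exceeds 80% under the plan's own d if the effect is sustained. Sizing a repeated-measures trial with a simple t-test is a common approximation and need not overstate power. This stands. A reader might infer from the mismatch that the trial is underpowered or has no primary analysis; the documents support neither.

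A second reply is that baseline is not ignored, because T0 and T1 enter the omnibus. That is correct, but they enter as outcomes, and nothing says how the post hoc between-arm tests use them.

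A third is that the benefit of the covariate depends on the comparator. This also stands. Against raw scores the gain is greatest at high correlation. Against change scores, a natural reading because the hypothesis is about decreases, it is only about 2 points at r = 0.7. Quoting one comparator alone would mislead.

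Finally, this is a feasibility trial, and an omnibus followed by Bonferroni tests is a recognised strategy. Even so, Section 4.4 makes an explicit 80% claim, Section 2 states a directional hypothesis, and the result is meant to inform a larger trial, so naming the estimate still matters.

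**Conclusion.** The point holds as a gap between the powered test and the planned analysis, and as a missing primary effect estimate. It should be fixed, but it is no reason to change the sample size. With 45 complete patients per arm and d = 0.6, readings of the post hoc tests that the text permits run from 49% power (change score, r = 0.3, divisor 3) to 95% (change score, r = 0.7, no correction). The stated 80% describes one undesignated case in that span. A single T1-adjusted contrast at .05 has higher power, and a narrower interval, than either unadjusted comparison at each correlation examined.

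These figures rest on the assumed correlations and divisors; the omnibus figures also need a sustained effect and compound symmetry. No gain is claimed for including the medication stratum. The case for it is consistency with Section 6.2. Handling of missing data is a separate question and is not judged here.

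**What to change.** In Section 8, make the primary between-arm analysis a model of ALS-18 at T2 to T4 with T1 as covariate, medication stratum as a factor, and arm-by-visit terms. The sponsor names one visit as the primary contrast, tested at .05 and reported with its 95% CI. The other two visits become secondary, estimated from the same model, with the Bonferroni family stated.

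In Section 4.4, keep the sample size and restate power for the named contrast over assumed correlations of 0.3 to 0.7.

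State that visits are timed from end of treatment, so every contrast compares arms six weeks apart since allocation. Timing alone therefore does not favour one visit over another, or over an average.

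Reconcile Section 6.3.2, which lists T1 before allocation, with Section 9.2, which lists allocation first, so that T1 is completed before allocation is known. This matters once T1 is a covariate.

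The cost is a protocol amendment notified to the METC and a small procedural clarification, with no new data, visits or patients. The trade-off is that the sponsor commits to one visit. The 84% to 98% applies to that visit only; the other visits in hypothesis (1) remain Bonferroni-tested.

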6.5 Replacement of individual subjects after withdrawal

Should patients withdraw from the study they will not be replaced.

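### The allowance behind 48 per arm counts pilot drop-out only, not the complete-case loss that listwise deletion creates; expected power is about 77–80%, not a secure 80%

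*Combined protocol and SAP*

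**What the plan says.** Section 4.4 sets out "to power this study at 80" per cent for a between-group d of 0.6, "using a significance level of .05 two tailed T-tests". It concludes: "The calculated sample size needed is 45 in each group". The pilot "showed a drop out 1 out of 15" and, after consultation with the pilot and audit group, "we expect a similar drop out rate in the current study". That gives 48 per arm and 96 in total.

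Four other rules decide who reaches the primary analysis:

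- Section 8 takes the ALS-18 at T0, T1, T2, T3 and T4 as the dependent variables and states: "Missing data from our primary outcome variable, will be listwise deleted". The same section later makes intention-to-treat the central analysis.
- Section 6.4.1 excludes patients who relapse and are admitted for more than one week.
- Section 6.5: "Should patients withdraw from the study they will not be replaced".
- Section 9.2 ends screening once 96 are included, 48 in each condition.

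On the pilot itself, section 4.4 uses a base of 15, while section 1 says that fourteen patients were assigned to baseline lengths. Table 1 prints no sample size.

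**The concern.** The 45 is the number needed in the analysis, so the step from 45 to 48 should cover every route by which a randomised patient leaves that analysis. It covers drop-out alone. Under listwise deletion over five waves, a patient who stays in the trial but misses one questionnaire is lost as surely as one who withdraws. With recruitment capped at 96 and no replacement, the allowance is the only protection.

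Table 1, printed as support for the calculation, shows signs of this loss in the pilot. At stake is whether the stated 80% describes what the plan's own rules are expected to deliver. The distinction between drop-out and analysis loss also matters because section 1 gives better retention estimates as a reason for running the trial.

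**Working it through.** **1. The plan's own figure.** Inputs from section 4.4: two-sample t-test, two-sided alpha 0.05, power 80%, d = 0.6. The noncentral t gives 44.6, rounded up to 45 per arm, with power 80.4% at 45. For the allowance, 45 × (1 + 1/15) = 48.0. Dividing instead gives 45/(14/15) = 48.2. With 48 enrolled and 1/15 lost, 48 × 14/15 = 44.8 remain, with power 80.2%. The stated figures reproduce, and the choice between multiplying and dividing is immaterial.

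**2. How many pilot patients had all waves.** Three readings of Table 1:

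- *Degrees of freedom.* The F statistic, printed as F(4.48), is read as 4 and 48 df over five waves: 4(n − 1) = 48 gives n = 13. Each paired t has 12 df, so n = 13.
- *p-values.* Five waves give 5 × 4/2 = 10 pairs. Ten times the two-sided p at 12 df is .0267, .0378 and .0059 for t = 3.77, 3.58 and 4.62, matching the printed .027, .038 and .006. At 13 df the values would be .0234, .0336 and .0048, which do not match.
- *Means.* If totals are whole numbers, 46.36 = 649/14, 35.43 = 496/14, 36.36 = 509/14 and 34.71 = 486/14. None of these four is possible with n = 13. The end-of-treatment mean, 35.54 = 462/13, is not possible with n = 14.

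So 14 patients appear to have been present before treatment and at every follow-up, and one of them missed the end-of-treatment wave. The contrasts between pre-treatment and follow-up still have 12 df, although each of those waves fits n = 14. This is what listwise deletion would produce.

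**3. Complete-case loss and power.** Analysable n = 48 × (1 − loss). Power is from the same t-test at d = 0.6.

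| Pilot base | Loss | Exact 95% CI | Analysable per arm | Power | Needed per arm for 45 complete |
|---|---|---|---|---|---|
| 15 (section 4.4) | 2/15 = 13.3% | 1.7% to 40.5% | 41.6 | 77.2% | 45/(13/15) = 51.9, i.e. 52 |
| 14 (section 1) | 1/14 = 7.1% | 0.2% to 33.9% | 44.6 | 80.0% | 45/(13/14) = 48.5, i.e. 49 |

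Rounded to whole patients, the first row is 76.5% at 41 and 77.6% at 42.

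**4. Exclusions under 6.4.1.** The documents give no rate for these, so they are not in the table. Any such loss beyond the pilot rate would lower both rows.

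**The case against.** The strongest reply is that the base of 15 may be the wrong one. Section 1 says fourteen were assigned, and the pre-treatment mean in Table 1 fits 14, so the fifteenth patient is absent from the table from the start. In this trial randomisation follows a four-week run-in (sections 6.3.2 and 9.2), and completing daily monitoring in that run-in is an inclusion criterion (4.2). A pilot loss before assignment would have no counterpart among the 96. On 14 the loss is 7.1%, close to the 6.7% assumed, and power stays at 80.0%. This stands. The documents do not say when the fifteenth patient left, so the result has to be a range.

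It is also fair that listwise deletion sits beside an intention-to-treat central analysis. If all available waves were used, one missed wave would not remove a patient. That shows the plan needs reconciling; it does not make the allowance match the deletion rule as written.

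Several stronger conclusions might be inferred, but the documents do not support them:

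- *That Table 1 shows 13 of 15.* It prints neither number. The 13 follows from its degrees of freedom, and the 15 comes from the text of 4.4.
- *That the drop-out figure is wrong, or half its true value.* One in 15 is reported as drop-out. Completeness over five waves is a different quantity.
- *That the trial will fall short of 45 per arm.* The intervals above are far too wide for that.
- *That non-replacement makes the allowance too small.* Inflating the sample is the normal answer to non-replacement. The operative rule is listwise deletion.
- *That the large RCT would inherit the planning figure.* Section 1 says this trial is meant to estimate retention, so it can pass on observed rates.

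**Conclusion.** Wrong as written, but minor. The arithmetic in 4.4 is sound. The fault is that the stated 80% is not supported by the plan's own analysis rules, because the allowance omits a loss that section 8 creates and that Table 1 appears to show.

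Expected power is about 77% on a base of 15 and 80.0% on a base of 14, so the cost is 0 to 3 points before any 6.4.1 exclusions. This assumes d = 0.6, the t-test used in 4.4, listwise deletion over all five waves, and that pilot completeness carries over. The last is the weakest assumption: the pilot's five waves were on a different schedule (4, 12 and 24 weeks of follow-up, against 8 and 16 here), and it had no psychoeducation patients. A figure below 77% would need a 6.4.1 rate that the documents do not give.

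**What to change.** Keep 96 patients.

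- **Section 4.4:** reconcile the pilot base with section 1 (14 or 15, and when the fifteenth patient left). State the allowance as complete-case loss under the listwise rule, not drop-out alone, and note that it comes from ImCT patients only. Restate expected power as about 77–80%, before 6.4.1 exclusions of unknown frequency.
- **Section 8:** reconcile listwise deletion with the intention-to-treat central analysis. A likelihood-based mixed model using all available waves would do this, and a single missed wave would then no longer remove a patient. If listwise deletion stays, the restated power range applies.
- **Reporting:** give drop-out, 6.4.1 exclusions and missed ALS-18 waves separately by arm, so that the large RCT can be planned on the right quantity.

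The cost is wording in two sections, a stated power up to about 3 points lower, and one more breakdown in the report. For comparison, protecting 45 complete cases on the base of 15 would take 52 per arm (104 in total, 8 more patients), which an effect of this size hardly justifies in a feasibility trial.
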